2.2 Secondary Objectives

- 1. To assess the impact of various funding models on vaccination coverage.
- 2. To evaluate a pharmacy-based strategy for recruiting participants for a patient-reported active adverse event following immunization surveillance system.

2.3 Primary Hypothesis:

 Vaccine coverage with all studied vaccines (high dose TIV, meningococcal B vaccine, meningococcal ACWY vaccine, Tdap, herpes zoster vaccine, and travel health vaccines) will increase significantly after implementation of the bundled pharmacist-delivery strategy. A significant increase will be defined as an increase of ≥10% vaccine coverage from preintervention levels.

2.4 Secondary Hypotheses:

- 1. The cost of a vaccine is a key factor in the individual's decision to be vaccinated. It is expected that vaccinations provided at no or minimal charge will have higher uptake than those that require more financial resources to obtain.
- 2. Knowledge about the vaccines studied is low among the general public, but higher among practitioners. There is a high level of support among both the public and health care providers for pharmacists as immunizers. Knowledge and support amongst both providers and the public will increase after implementation of the program.

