3 STUDY DESIGN

3.1 Vaccine Coverage

There are numerous barriers that impede an individual from becoming vaccinated. A successful intervention should incorporate a multi-faceted approach to improve vaccine uptake. By combining, or bundling different communication strategies, financial incentives and promoting awareness about vaccines and who can administer them, this study seeks study seeks to improve uptake in vaccines with low coverage rates.

ROMEO File #: 1021559

To assess the effectiveness of bundled pharmacist-delivery strategy and to assess the impact of various funding models on vaccination coverage, a demonstration program implementation and evaluation project will be conducted in two New Brunswick and two Nova Scotia communities. One community in each province will serve as an intervention community in which implementation strategies specifically designed for each of the target vaccines will be used. One of the communities in each province will serve as the non-intervention control arm where immunization practice will continue unchanged.

It is hypothesized that vaccine coverage will increase significantly, defined as an increase of $\geq 10\%$ vaccine coverage from pre-program levels, after implementation of the pharmacist-delivery strategy. As public funding of vaccination is a key factor in individuals' decision-making with respect to vaccination, it is also expected that vaccinations provided at no or minimal charge will have higher uptake than those that require more financial resources to obtain.

All pharmacies in the intervention and control communities have been identified using data from Pharmacy Association of Nova Scotia and the New Brunswick Pharmacists' Association. Pharmacies interested in being involved with this research will serve on an advisory board with investigators for logistical and organizational purposes. Pharmacists employed at participating pharmacies will act as non-academic members of the research team who will deliver the targeted vaccines. All pharmacists receive training and certification in vaccine administration through provincial regulatory authorities. Members of the research team will provide additional support to pharmacists involved in the study to reinforce best practice strategies. Pharmacists in intervention communities will provide vaccines through bundling of different communication strategies and payment mechanisms depending on the vaccine.

Pharmacist Intervention Strategies:

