- 1. *Communication Strategies* Pharmacists and pharmacy staff in intervention communities will use various public communication strategies, including:
 - a. targeted mail outs and/or phone calls by pharmacies to individuals in their databases based on risk factors for contracting and/or transmitting vaccine-preventable disease (e.g., immunosuppressant medications, recent birth in family)
 - b. timed marketing linked to other vaccine clinics (e.g., influenza clinics) and awareness campaigns (e.g., back-to-school advertising)
- 2. *Payment mechanisms* Intervention communities will provide vaccine through the following payment mechanisms, based on the study vaccine:
 - a. universal vaccination with "publicly funded" vaccine (vaccine provided to individual without charge (i.e. Tdap vaccine))
 - vaccination using a co-pay model (individuals receive vaccine at no cost after paying a designated co-pay fee comprised of the pharmacy dispensing fee and any administration fee charged by the pharmacist immunizers (i.e. high-dose TIV); and
 - c. vaccination using the current private market model where vaccine would be purchased either by the recipient or through insurance (standard of care control arm, (i.e. Meningococcal serogroup B, Meningococcal serogroup ACWY and highdose TIV influenza, herpes zoster, and travel health vaccines).

The non-intervention control arm will be the current model wherein a patient specifically requests a vaccination or the pharmacist offers this option while the patient is in the pharmacy. This non-intervention arm will be compared to the intervention arm.

Inclusion criteria

Inclusion criteria for the selection of the four communities include population size (approximately 30,000 adults >18 years of age), stable population, service by a centralized regional hospital and local community hospitals, availability of community pharmacies, interest and availability of community pharmacists (sufficient numbers of pharmacists qualified to provide vaccinations), and lack of substantial health care spill over to adjacent communities. Spill over is defined as a pattern of health-care utilization where patients regularly receive care at different regional health centres. Communities will be geographically separated to minimize potential spill over.

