Based on this inclusion criteria, four communities were selected. Intervention communities in which the communication and payment strategies will be implemented are: Saint John, New Brunswick and New Glasgow/Pictou/Antigonish, Nova Scotia area, which include the smaller towns of Stellarton and Westville, Nova Scotia. Control communities where pharmacy delivered immunizations will be offered under their current model are: Moncton, New Brunswick and Kentville/New Minas/Wolfville, Nova Scotia, which include the smaller towns of Canning and Coldbrook, Nova Scotia. Intervention and control communities will be compared to one another to assess the effectiveness of the bundled strategies.

Payment mechanisms will be applied in intervention communities, excluding no client from this strategy. Communication strategies will be targeted based on the type of vaccine a client is eligible to receive. Pharmacists will contact clients over the age of 65 by phone or mail out to recommend high-dose TIV and contact clients who are 50 and older to recommend herpes zoster. Clients who are immunosuppressed may also receive phone calls/mail outs for vaccines against meningococcal disease. Individual eligibility will also be assessed by pharmacists during consultations. Through client's interaction to fill prescriptions, pharmacists have regular contact with high-risk individuals and are able to proactively and systematically review patients' medical histories and medications to remind them of the benefits of specific vaccinations. They can also implement awareness campaigns during travel season and school breaks to target clients who may be travelling to high-risk areas and should consider getting vaccinated to protect themselves against travel-related illnesses, such as Hepatitis A and Typhoid Fever.

Measurement of vaccine coverage

Vaccine coverage rates will be measured using the following:

- **1.** pharmacy database analysis,
- 2. public health vaccine reports by physicians,
- 3. number of vaccine doses delivered to pharmacies in all four regions, and
- 4. public survey within the study communities to determine immunization status.

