Pharmacy databases will be used to determine the number of doses administered to individuals relative to the total number of clients in the pharmacy database in the eligible age range. The total number of doses administered by pharmacists (from their database) plus the number administered by family physicians, through study-specific reciprocal notification forms, will also be calculated and compared to

ROMEO File #: 1021559

the Statistics Canada population age-specific census data for the community will also be calculated. The study-specific system of reciprocal notification forms for family physicians will be implemented so that it is similar to that used for publicly funded routine pediatric vaccines. Another estimate of vaccine coverage will be vaccine doses distributed to pharmacies in the participating communities (obtained from the manufacturer and Public Health) relative to the eligible population based on Statistics Canada census data from 2016. Specific questions about receipt of target vaccines will be added to the KABB survey that will be administered pre- and post-intervention. These questions will be modeled on a 2014 study performed by the Vaccine Evaluation Center (Schneeberg, 2014). The KABB survey will also include specific questions about willingness to pay to inform decisions about co-payment funding models for recommended adult vaccines.

Outcomes

As a result of this study:

- 1. Population specific vaccine coverage will be documented before and after program implementation interventions.
- 2. The proportion of the population in intervention districts whose supplementary health benefit plans cover studied vaccines will be identified.
- 3. The public willingness to pay and co-pay for studied vaccines will be better known and understood.

For specific outcomes related to each targeted vaccine, see appendices.

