determined by physician billing data and public health provision of vaccine to physicians relative to the Statistics Canada population age specific census data for that community. A study-specific system of reciprocal notification forms for family doctors will be implemented that is similar to that used for publicly funded routine vaccines. A third estimate of vaccine coverage will be vaccine doses distributed in the participating communities (obtained from the manufacturer) relative to the eligible population based on Statistics Canada census data (2011 and 2016 when available). The fourth estimate of vaccine coverage will be derived from the pre- and postprogram public survey. Binomial point estimates and confidence intervals will be made for vaccine coverage rate within site, and coverage will be compared between and among sites using confidence intervals for the difference of binomial proportions, Fisher's exact tests, and logistic regression. Using a margin of superiority of 10%, when comparing two coverage proportions within site or between sites, a sample size of 298 per group gives 80% power to conclude in favor of superiority when the true difference in proportions is at least 20%, and a sample size of 1209 per group provides 80% power when the true difference in proportions is at least 15%, assuming independent responses. However, it is anticipated that there will be dependence within the family unit regarding the decision to be vaccinated, in which case the precision on the binomial point estimate, and thereby, the required sample size, depends on the size of the family unit and the intraclass correlation. Assuming the family unit to consist of two adults, and under the worst-case scenario in which the decision on vaccination is fully concordant for the two family members, the required sample size per group to detect a specified difference is doubled, to 596 (2418) when the true difference is at least 20% (15%). Estimates of the intraclass correlation will be calculated using data from pharmacy databases and from the public survey portion of the study, and these will be used to adjust confidence intervals and test statistics to accommodate within family dependence (Donner, Brikett, & Buck, 1981).

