APPENDIX A-E DELETED FOR PRIVACY REASONS

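### Payment model, promotion and target group all vary by vaccine, so higher uptake of free or low-charge vaccines (secondary hypothesis 1) cannot be attributed to cost

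*Combined protocol and SAP*

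**What the plan says.** Secondary objective 1 (section 2.2) is to assess how funding models affect coverage. Secondary hypothesis 1 (section 2.4) opens by calling cost a key factor in the decision to be vaccinated and then predicts: "It is expected that vaccinations provided at no or minimal charge will have higher uptake than those that require more financial resources to obtain". Section 3.1 repeats the prediction.

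Section 3.1 sets payment by vaccine: "Intervention communities will provide vaccine through the following payment mechanisms, based on the study vaccine". Tdap is free, high-dose TIV is co-pay, and the two meningococcal vaccines, herpes zoster and travel vaccines are private market. It describes promotion in the same way. In each intervention community, "implementation strategies specifically designed for each of the target vaccines will be used", and "Communication strategies will be targeted based on the type of vaccine a client is eligible to receive". Pharmacists will, for example, "contact clients over the age of 65 by phone or mail out to recommend high-dose TIV"; for zoster the contact age is 50 and older.

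For coverage, section 6.2 item 3 says that "coverage will be compared between and among sites using confidence intervals for the difference of binomial proportions", together with Fisher's exact tests and logistic regression. It names no contrast by funding model. For vaccine-specific outcomes section 3.1 points elsewhere: "For specific outcomes related to each targeted vaccine, see appendices". The public file carries only the notice "APPENDIX A-E DELETED FOR PRIVACY REASONS".

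**The concern.** Hypothesis 1 compares different vaccines. Those vaccines differ in price, and also in what they prevent, whom they are meant for, how they were promoted and how well they were already taken up. A gap between the free, co-pay and private-market tiers could come from any of these.

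The synopsis expects public health to use the results when deciding on funding. A table showing higher uptake of Tdap than of, say, zoster vaccine would invite the conclusion that removing the charge caused the difference. As worded, objective and hypothesis encourage that reading.

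**Working it through.** The plan gives no figure for the funding comparison, so there is nothing of its own to reproduce. Its sample sizes (298 and 1209 per group) concern coverage differences within or between sites. Its 10% figures are an increase from pre-intervention levels and a superiority margin; neither is a threshold between funding tiers. The question is what the design can separate.

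**Inputs, all from section 3.1**

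| Vaccine | Payment in intervention communities | Promotion or target group in the body text |
|---|---|---|
| Tdap | free | no contact rule of its own; a recent birth is one example in the general list |
| High-dose TIV | co-pay | phone or mail to clients over 65 |
| Herpes zoster | private market | contact with clients aged 50 and older |
| Meningococcal B, ACWY | private market | immunosuppressed clients may be contacted |
| Travel vaccines (one group) | private market | campaigns around travel season and school breaks |

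Control communities keep current practice without the added promotion. I take high-dose TIV as co-pay in the intervention communities and private market in control; this is an assumption.

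**Step 1: the hypothesis as worded.** Take uptake of six vaccines in the intervention communities. Six vaccine levels plus a free effect and a co-pay effect make 8 parameters; the rank is 6. Both payment effects are fully aliased with vaccine.

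**Step 2: add control and pre-program data.** For vaccine v, let

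net change(v) = (post − pre, intervention) − (post − pre, control).

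If coverage would otherwise have moved in parallel in the two arms, then

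- net change(Tdap) = C(Tdap) + F(free)
- net change(high-dose TIV) = C(high-dose TIV) + F(co-pay)
- net change(v) = C(v) for the four private-market vaccines

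Here C is the communication effect and F the funding effect. Six net changes face eight unknowns. The sums, which are the bundle effects, are estimable. The two F terms alone are not.

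**Step 3: the same as ranks.** There are 6 vaccines × 2 arms × 2 periods = 24 cells. Parameters are 12 baselines, 6 trends, the C terms and 2 funding effects. Separate communities give 48 cells and 24 baselines.

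| Assumption | Rank of parameters, by arm | Rank of parameters, by community | F estimable? | Bundle effects estimable? |
|---|---|---|---|---|
| C differs by vaccine | 24 of 26 | 36 of 38 | neither | yes |
| One common C | 21 of 21 | 33 of 33 | both | yes |
| One common C, Tdap already free in both arms before the program | 20 of 21 | 32 of 33 | co-pay only | all but Tdap's funding part |
| C differs by vaccine, trends differ by arm | 24 of 32 | 36 of 44 | neither | no |

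**Step 4: size of the error.** Suppose the net change of a private-market vaccine is subtracted from that of Tdap:

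[C(Tdap) + F(free)] − C(private) = F(free) + d, where d = C(Tdap) − C(private).

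The plan gives no value for d. For assumed values of −10, −5, 0, 5 or 10 points, the apparent funding effect is off by −10, −5, 0, 5 or 10 points.

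**The case against.** **The hypothesis only predicts an ordering.** Read alone, the quoted sentence does. But the same item opens with cost as a driver of the decision, and the objective it serves is the impact of funding models. The causal reading comes from the plan's own wording.

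**Bundling is a declared choice.** This stands. The study is a demonstration program and its primary objective evaluates the bundle. A reader might infer that the confounding undermines that objective too. It does not, because the bundle effect does not require payment and promotion to be separated.

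**The appendices may hold the missing analysis.** This stands as a limit. A reader might infer that the plan has no analysis by funding model. Only the body text can be said to lack one.

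**Promotion may differ less than claimed.** Partly stands. Section 3.1 gives one common list of communication methods and no contact rule specific to Tdap, so d may be small. But the section also says that strategies are designed per vaccine, and nothing states that their effects are equal. Age-specific eligible denominators make coverage comparable as a rate; they do not make the target groups alike.

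**The ranks and the values of d hold by construction.** Agreed. They show which assumption does the work and are not evidence that bias is present.

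**The private-market contrast can be legitimate.** Agreed. It identifies a funding effect under a common communication effect and may be reported with that assumption stated.

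**The recommended net change has its own assumptions.** Agreed. It fails if trends differ by arm, and there are two communities per arm.

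**Conclusion.** On the body text, the comparison in secondary hypothesis 1 cannot be attributed to cost and does not by itself answer secondary objective 1. The free and co-pay tiers hold one vaccine each, and both funding effects are inseparable from vaccine-specific communication (24 of 26, or 36 of 38 by community). What can be estimated is each vaccine's bundle effect against control, given parallel trends. A funding effect needs two further things: equal communication effects across vaccines and, for Tdap, a program that changed its funding status relative to control. The size of any misattribution equals d, which the documents do not give.

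Two further inferences are not supported. The listing of high-dose TIV under both co-pay and private market is not shown to be a contradiction, because the private-market item is labelled as the standard-of-care control arm. The remark in section 1.2 that Tdap is funded in most provinces does not show that it was already free in the study communities.

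The point concerns one secondary objective. It is worth correcting because the results are meant to inform funding decisions.

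**What to change.** In sections 2.2, 2.4 and 6.2:

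- Base secondary objective 1 on each vaccine's net change in coverage (intervention minus control, post minus pre), and interpret it as the effect of that vaccine's payment-plus-communication bundle.
- Use the coverage sources that have a pre-program measurement. The public survey is planned before and after. The notification forms for family physicians are introduced by the study, and no baseline from them is shown.
- State the parallel-trends assumption, and that two communities per arm limit what the confidence interval can convey.
- Tabulate net change by funding tier and label differences between tiers as descriptive, not as an effect of cost.
- If Tdap or high-dose TIV is contrasted with the private-market vaccines, present it as exploratory. State that it assumes equal communication effects across vaccines and, for Tdap, that the program changed its funding status relative to control.

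This costs a rewording of one objective and one hypothesis and a short paragraph in section 6.2. Coverage before and after the program is already an outcome. The downside is a weaker causal claim about funding.

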3 STUDY DESIGN

3.1 Vaccine Coverage

There are numerous barriers that impede an individual from becoming vaccinated. A successful intervention should incorporate a multi-faceted approach to improve vaccine uptake. By combining, or bundling different communication strategies, financial incentives and promoting awareness about vaccines and who can administer them, this study seeks study seeks to improve uptake in vaccines with low coverage rates.

ROMEO File #: 1021559

To assess the effectiveness of bundled pharmacist-delivery strategy and to assess the impact of various funding models on vaccination coverage, a demonstration program implementation and evaluation project will be conducted in two New Brunswick and two Nova Scotia communities. One community in each province will serve as an intervention community in which implementation strategies specifically designed for each of the target vaccines will be used. One of the communities in each province will serve as the non-intervention control arm where immunization practice will continue unchanged.

It is hypothesized that vaccine coverage will increase significantly, defined as an increase of $\geq 10\%$ vaccine coverage from pre-program levels, after implementation of the pharmacist-delivery strategy. As public funding of vaccination is a key factor in individuals' decision-making with respect to vaccination, it is also expected that vaccinations provided at no or minimal charge will have higher uptake than those that require more financial resources to obtain.

All pharmacies in the intervention and control communities have been identified using data from Pharmacy Association of Nova Scotia and the New Brunswick Pharmacists' Association. Pharmacies interested in being involved with this research will serve on an advisory board with investigators for logistical and organizational purposes. Pharmacists employed at participating pharmacies will act as non-academic members of the research team who will deliver the targeted vaccines. All pharmacists receive training and certification in vaccine administration through provincial regulatory authorities. Members of the research team will provide additional support to pharmacists involved in the study to reinforce best practice strategies. Pharmacists in intervention communities will provide vaccines through bundling of different communication strategies and payment mechanisms depending on the vaccine.

Pharmacist Intervention Strategies:

- 1. *Communication Strategies* Pharmacists and pharmacy staff in intervention communities will use various public communication strategies, including:
 - a. targeted mail outs and/or phone calls by pharmacies to individuals in their databases based on risk factors for contracting and/or transmitting vaccine-preventable disease (e.g., immunosuppressant medications, recent birth in family)
 - b. timed marketing linked to other vaccine clinics (e.g., influenza clinics) and awareness campaigns (e.g., back-to-school advertising)
- 2. *Payment mechanisms* Intervention communities will provide vaccine through the following payment mechanisms, based on the study vaccine:
 - a. universal vaccination with "publicly funded" vaccine (vaccine provided to individual without charge (i.e. Tdap vaccine))
 - vaccination using a co-pay model (individuals receive vaccine at no cost after paying a designated co-pay fee comprised of the pharmacy dispensing fee and any administration fee charged by the pharmacist immunizers (i.e. high-dose TIV); and
 - c. vaccination using the current private market model where vaccine would be purchased either by the recipient or through insurance (standard of care control arm, (i.e. Meningococcal serogroup B, Meningococcal serogroup ACWY and highdose TIV influenza, herpes zoster, and travel health vaccines).

The non-intervention control arm will be the current model wherein a patient specifically requests a vaccination or the pharmacist offers this option while the patient is in the pharmacy. This non-intervention arm will be compared to the intervention arm.

Inclusion criteria

Inclusion criteria for the selection of the four communities include population size (approximately 30,000 adults >18 years of age), stable population, service by a centralized regional hospital and local community hospitals, availability of community pharmacies, interest and availability of community pharmacists (sufficient numbers of pharmacists qualified to provide vaccinations), and lack of substantial health care spill over to adjacent communities. Spill over is defined as a pattern of health-care utilization where patients regularly receive care at different regional health centres. Communities will be geographically separated to minimize potential spill over.

Based on this inclusion criteria, four communities were selected. Intervention communities in which the communication and payment strategies will be implemented are: Saint John, New Brunswick and New Glasgow/Pictou/Antigonish, Nova Scotia area, which include the smaller towns of Stellarton and Westville, Nova Scotia. Control communities where pharmacy delivered immunizations will be offered under their current model are: Moncton, New Brunswick and Kentville/New Minas/Wolfville, Nova Scotia, which include the smaller towns of Canning and Coldbrook, Nova Scotia. Intervention and control communities will be compared to one another to assess the effectiveness of the bundled strategies.

Payment mechanisms will be applied in intervention communities, excluding no client from this strategy. Communication strategies will be targeted based on the type of vaccine a client is eligible to receive. Pharmacists will contact clients over the age of 65 by phone or mail out to recommend high-dose TIV and contact clients who are 50 and older to recommend herpes zoster. Clients who are immunosuppressed may also receive phone calls/mail outs for vaccines against meningococcal disease. Individual eligibility will also be assessed by pharmacists during consultations. Through client's interaction to fill prescriptions, pharmacists have regular contact with high-risk individuals and are able to proactively and systematically review patients' medical histories and medications to remind them of the benefits of specific vaccinations. They can also implement awareness campaigns during travel season and school breaks to target clients who may be travelling to high-risk areas and should consider getting vaccinated to protect themselves against travel-related illnesses, such as Hepatitis A and Typhoid Fever.

Measurement of vaccine coverage

Vaccine coverage rates will be measured using the following:

- **1.** pharmacy database analysis,
- 2. public health vaccine reports by physicians,
- 3. number of vaccine doses delivered to pharmacies in all four regions, and
- 4. public survey within the study communities to determine immunization status.

Pharmacy databases will be used to determine the number of doses administered to individuals relative to the total number of clients in the pharmacy database in the eligible age range. The total number of doses administered by pharmacists (from their database) plus the number administered by family physicians, through study-specific reciprocal notification forms, will also be calculated and compared to

ROMEO File #: 1021559

the Statistics Canada population age-specific census data for the community will also be calculated. The study-specific system of reciprocal notification forms for family physicians will be implemented so that it is similar to that used for publicly funded routine pediatric vaccines. Another estimate of vaccine coverage will be vaccine doses distributed to pharmacies in the participating communities (obtained from the manufacturer and Public Health) relative to the eligible population based on Statistics Canada census data from 2016. Specific questions about receipt of target vaccines will be added to the KABB survey that will be administered pre- and post-intervention. These questions will be modeled on a 2014 study performed by the Vaccine Evaluation Center (Schneeberg, 2014). The KABB survey will also include specific questions about willingness to pay to inform decisions about co-payment funding models for recommended adult vaccines.

Outcomes

As a result of this study:

- 1. Population specific vaccine coverage will be documented before and after program implementation interventions.
- 2. The proportion of the population in intervention districts whose supplementary health benefit plans cover studied vaccines will be identified.
- 3. The public willingness to pay and co-pay for studied vaccines will be better known and understood.

For specific outcomes related to each targeted vaccine, see appendices.

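### The two census-based coverage estimates divide all doses by residents only, so non-residents drawn by the subsidised offer would raise coverage in the intervention communities alone, after launch

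*Combined protocol and SAP*

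**What the plan says.** **The offer.** Section 3.1 makes Tdap free in the intervention communities and puts high-dose TIV on a co-pay basis: "individuals receive vaccine at no cost after paying a designated co-pay fee". On who may use these terms it says: "Payment mechanisms will be applied in intervention communities, excluding no client from this strategy". For the other arm: "One of the communities in each province will serve as the non-intervention control arm where immunization practice will continue unchanged".

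**The measurement.** Section 3.1 lists four sources of coverage, and two use a census denominator.

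- Doses administered: "The total number of doses administered by pharmacists (from their database) plus the number administered by family physicians" (the latter from study notification forms), of which a comparison with "the Statistics Canada population age-specific census data for the community will also be calculated".
- Doses distributed to community pharmacies, over the eligible census population. Section 6.2 repeats this one as "vaccine doses distributed in the participating communities".

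The other two are the pharmacy-database estimate, whose denominator is the pharmacies' own clients of eligible age, and the public survey in the study communities. No estimate is designated primary.

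**The safeguard.** Communities are chosen for a stable population, geographic separation and lack of substantial spill-over. "Spill over is defined as a pattern of health-care utilization where patients regularly receive care at different regional health centres".

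**The concern.** A coverage proportion requires the people counted above the line to be a subset of those below it. In the two census-based estimates they need not be. Someone from a surrounding area who is vaccinated at an intervention pharmacy is counted as covered without belonging to the population being covered.

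Ordinary non-resident use can occur in both arms and both periods, and would largely cancel in a before-after comparison. Inflow prompted by the offer does not cancel, because the price advantage exists only in the intervention communities and only after launch. It would add to both the before-after rise and the intervention-control difference, which serve primary objective 1. It would also be concentrated in the free and co-pay vaccines, which favours secondary hypothesis 1. The plan's own reasoning, that cost is a key factor in the decision to be vaccinated, makes such inflow plausible.

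The spill-over criterion concerns habitual use of regional health centres. It does not address a single pharmacy visit prompted by a subsidy.

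**Working it through.** **Inputs from the documents.** About 30,000 adults per community (section 3.1, inclusion criteria); success defined as a rise of at least 10% (section 2.3); superiority margin of 10% with 298 or 1,209 per group, doubled to 596 or 2,418 for family concordance (section 6.2); adult Tdap coverage well under 10% (section 1.2).

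**Assumed.** The share *s* of counted doses that go to non-residents, for which the documents give no value; coverage before and after; and the size of the over-65 group.

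**1. The plan's own figures.** Use *n* = [p1(1−p1) + p2(1−p2)] × (1.645 + 0.842)² / (difference − 0.10)², with one-sided alpha 0.05 and 80% power.
- 0.40 vs 0.60: 0.48 × 6.183 / 0.01 = 297 (stated 298).
- 0.425 vs 0.575: 0.48875 × 6.183 / 0.0025 = 1,209 (stated 1,209).

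One-sided 0.025 gives 377 and 1,535 and does not match. The sample sizes are not in dispute and do not depend on residence.

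**2. Doses per point.** Points added = non-resident doses / eligible residents.
- All 30,000 adults eligible: 300 / 30,000 = 1 point; 3,000 / 30,000 = 10 points, the whole threshold.
- Over-65 group assumed to be 15% to 25% of 30,000 (4,500 to 7,500 people): 45 to 75 doses = 1 point.

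**3. Illustrative rise.** Assume 5% before and 15% observed after (0.15 × 30,000 = 4,500 recipients).

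| *s* | Resident coverage after, 15(1−s) | Rise if *s* applies after launch only, 15(1−s) − 5 | Rise if *s* is the same in both periods, (15−5)(1−s) |
|---|---|---|---|
| 10% | 13.5% | 8.5 points | 9.0 points |
| 20% | 12.0% | 7.0 points | 8.0 points |
| 30% | 10.5% | 5.5 points | 7.0 points |

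**4. Share needed to turn a true 5-point rise into 10.** With the share applying after launch only, s = 1 − (before + 5)/(before + 10).
- 5% before: 1 − 10/15 = 33%.
- 10% before: 1 − 15/20 = 25%.
- 40% before: 1 − 45/50 = 10%.

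**5. Effect on the superiority test.** Apparent coverage = true coverage/(1−s) in the intervention arm only. Suppose the true difference equals the 10% margin, with 596 per group and full pair concordance (596/2 = 298 effective). The one-sided 5% test then rejects as follows.

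| True coverage | s = 0 | 5% | 10% | 20% |
|---|---|---|---|---|
| 20% vs 10% | 5% | 9.9% | 18.5% | 49.8% |
| 50% vs 40% | 5% | 16.0% | 39.3% | 93.2% |

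This treats coverage as a sampled proportion at the plan's planning size. It shows sensitivity and does not forecast the result.

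**The case against.** Much can be said for the plan.

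- Two of the four estimates avoid the census mismatch and can cross-check the others. This stands, with limits: a newcomer who registers in order to be vaccinated adds one to both parts of the pharmacy-database ratio, which still raises it slightly, and the survey recruits through open advertisements.
- The price draw concerns two vaccines only; meningococcal, zoster and travel vaccines stay on the private market. Section 1.2 says Tdap is already funded for adults in most provinces, so the pull of free Tdap may be weak. This stands.
- Geographic separation limits movement between study communities. It does, but it does not address inflow from the areas around each one.
- Residents vaccinated elsewhere, doses at non-participating pharmacies and unreturned physician forms lower the administered-dose estimate. This stands.
- Appendices A to E were removed, so a residence rule there cannot be excluded.

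A reader might infer that measured coverage as a whole must be too high in the intervention arm, or that the 10% criterion would be met only because of non-residents. The documents support neither. Nothing fixes *s*, and the illustration places observed coverage exactly on the threshold, so any positive share misses it. Nor does section 6.2 fully match section 3.1: its second estimate names physician billing and public health supply to physicians, without pharmacist doses.

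**Conclusion.** The concern holds for the doses-administered estimate in section 3.1 and the doses-distributed estimate in sections 3.1 and 6.2. As written, their numerators are not limited to the people in their denominators, and the part of the error caused by the offer falls on the intervention communities after launch.

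That component is upward. The net error in the administered-dose estimate is not certain, because missed doses work against it. The size cannot be found from the documents. The conclusion rests on there being no residence rule in the removed appendices, and on some draw from the free or co-pay terms. The change is worth making because it is cheap and turns an untested assumption into a measured quantity. Nothing here shows that the primary comparison is invalid.

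**What to change.** Leave the offer unchanged. In sections 3.1 and 6.2:

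1. Define the census area that forms the denominator for each community.
2. Record a resident/non-resident flag, derived from postal code, in the pharmacy extract and on the physician notification form.
3. In all four communities and both periods, count only resident recipients in the doses-administered census estimate, with the all-doses figure as a sensitivity analysis.
4. Report non-resident recipients by arm and period, as a direct measure of draw-in.
5. Multiply the doses-distributed estimate by the resident share seen in the records, or label it as not being resident coverage.
6. Reconcile the second estimate in section 6.2 (physician data only) with the pharmacist-plus-physician count in section 3.1.

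Cost: ethics board approval for one extra field, which section 5.1 requires for any protocol change and which touches client data although the stated participants are pharmacies. Some postal codes will be missing, and reported coverage will be somewhat lower. Residents' doses received elsewhere remain uncounted, so the restricted estimate should be described as leaning low on that account.
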